Version # and Date:	Version 7 Dated 2020-02-04						
Clinical Phase:	Phase 3						
Investigational Drugs:	Low titer, platelet replete-leukocyte reduced, group O whole blood						
Trial Site:	University of Pittsburgh						
IND Sponsor:	[name], MPH						
Investigator:	[name], MPH						
Co-Principal	[name]						
Investigator							
Sub-Investigators:	[name] [name]; [name]; [name], PhD; [name]						
Research Facilities:	UPMC Presbyterian/ Montefiore						
Clinical Laboratories:	UPMC Presbyterian Shadyside CP PUH- UPMC Clinical Laboratory Building						
Study Rationale:	Initiation of whole blood resuscitation in the prehospital setting and continued through the in-hospital phase of treatment to patients in hemorrhagic shock represents the most efficacious and ideal intervention post-injury.]					
Study Objectives:	The objective of this study is to determine whether LTLR-WB resuscitation in the prehospital setting with continuation through the in-hospital acute resuscitation phase of care will significantly reduce the morbidity and mortality attributable to hemorrhagic shock post-injury as compared to standard prehospital and in-hospital resuscitation practice.						
Study Hypothesis:	Early whole blood transfusion initiated in the prehospital settin and continued through the in-hospital acute resuscitation phase of treatment will reduce the morbidity and mortality attributable to hemorrhagic shock post-injury as compared to standard prehospital and in-hospital resuscitation practice	ıg					
Study Aims:	Specific Aim I: Determine the feasibility and most appropriate study population that will lead to a large multicenter clinical tria designed to evaluate the effectiveness of prehospital through in-hospital LTLR-WB as compared to standard care practice in patients at risk of hemorrhagic shock. Specific Aim II: Determine if prehospital through in-hospital LTLR-WB reduces 28-day mortality, multiple organ dysfunction, presenting coagulopathy, 24-hour resuscitation requirements and early mortality time points as compared to	al n					

1. OBJECTIVE, SPECIFIC AIMS, BACKGROUND, AND SIGNIFICANCE

1.1 **OBJECTIVE**

The objective of this study is to determine whether LTLR-WB resuscitation in the prehospital setting with continuation through the in-hospital acute resuscitation phase of care will significantly reduce the morbidity and mortality attributable to hemorrhagic shock post-injury as compared to standard prehospital and in-hospital resuscitation practice.

1.2 SPECIFIC AIMS

Hypothesis: The initiation of LTLR-WB resuscitation in the prehospital setting with continuation through the in-hospital acute resuscitation phase of care will significantly reduce the morbidity and mortality attributable to hemorrhagic shock post-injury as compared to standard prehospital and in-hospital resuscitation practice.

Specific Aims:

Specific Aim I: Determine the feasibility and most appropriate study population that will lead to a large multicenter clinical trial designed to evaluate the effectiveness of prehospital through inhospital LTLR-WB as compared to standard care practice in patients at risk of hemorrhagic shock.

Specific Aim II: Determine if prehospital through in-hospital LTLR-WB reduces 28-day mortality, in-hospital mortality, multiple organ dysfunction, presenting coagulopathy, 24-hour resuscitation requirements and early mortality as compared to standard of care prehospital and in-hospital resuscitation in patients at risk of hemorrhagic shock.

Specific Aim III: Determine the primary drivers by which prehospital through in-hospital LTLR-WB improves clinical, resuscitative and hemostatic outcomes as compared to standard of care prehospital and in-hospital resuscitation in patients at risk of hemorrhagic shock.

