lactate and shock index (SI, heart rate/systolic blood pressure-bpm/mmHg) 4) Acute Respiratory Distress Syndrome (ARDS): We will compare pulmonary dysfunction using the Berlin definition for ARDS.⁸⁶ 5) Nosocomial Infection (NI): We will compare the incidence of pneumonia and blood stream infections. 6) Mortality: We will compare mortality rates at 3, 6 and 24 hours following arrival, all cause in-hospital and 28-day mortality. 7) Blood component transfusion and resuscitation requirements at 24 hours: We will compare overall blood component transfusion requirements and crystalloid/colloid resuscitation requirements across the two arms. 8) Acute Hemolytic Transfusion Reaction (AHTR): We will compare the incidence of AHTRs across study arms as defined by the CDC/National Healthcare Safety Network (NHSN) Hemovigilance Surveillance definition. (www.cdc.gov/nhsn) Length of hospital stay and intensive care unit stay. Length of stay and ICU resources will be descriptively compared. Patients will be followed for 28 days from admission for the 28-day mortality outcome utilizing chart review, patient contact or utilization of the social security death index for those who cannot be contacted.

Predefined Subgroup Analyses: Predefined subset analyses for the pilot trial will be performed looking at our primary outcomes (safety/efficacy and feasibility) in 1) Females > 50 years of age versus study cohort with females < 50 years excluded ; 2) Patients who ultimately did or did not require in-hospital blood transfusion; 3) Patients with and without significant traumatic brain injury (Head abbreviated injury score- AIS >2); 4) Patients enrolled from the scene of injury versus those enrolled from a referral hospital; 5) Patients that require operative intervention in the first 24 hours; 6) Those patients with a preinjury history of anticoagulation / antiplatelet therapy; 7) Patients who ultimately did or did not require massive transfusion (≥ 10 units blood in first 24 hrs) 8)Patients who did or did not receive prehospital PRBCs.

Clinical Outcome Definitions:

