Mechanistic Outcomes: The principle factors that may be responsible for beneficial clinical outcome effects associated with or attributable to LTLR-WB resuscitation when initiated early in the prehospital phase of injury are an important and essential objective of the proposed pilot trial. We will compare across treatment arms: 1) Coagulopathy: Coagulopathy will be assessed via PT/PTT/INR and rapid Thromboelastography (r-TEG) measurements. 2) Platelet Function: We will assess platelet activation, aggregation, and adhesion via flow cytometry analysis, whole blood aggregometry measurements and flow chamber analysis under shear stress conditions, respectively in a subset of patients.^{88,89} 3) Glycocalyx integrity: We will assess glycocalyx integrity by measuring serum concentrations of Syndecan-1 and Hyaluronan by ELISA at inhospital time points. 3) Donor Exposure, Age and Volume of Transfusion Products: During the prehospital and in-hospital acute resuscitation phase of the study the number donors from all transfused products blood products, the age of all LTLR-WB and PRBCs from the standard of care arm and overall transfusion volumes will be recorded and compared.

Blood Sampling and In-Hospital Measurements: In-hospital phase blood sampling will occur upon arrival (+ 4 hrs) and at 12 hours (+/- 12hrs) and 24 hours (+/- 12hrs) from time of arrival. Timing of samples will need to be flexible based upon patient availability and logistic factors. This early in-hospital sampling will allow adequate assessment of the benefits of early LTLR-WB resuscitation and appropriate characterization of the proposed clinical and mechanistic outcomes. TEG analysis at arrival, 12hr and 24hr time points will be performed on a TEG[®] 5000 Thromboelastograph[®] Hemostasis Analyzer.

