Statistical Distributions of Enrolled Sample of Patients: Descriptive statistics, including means, standard deviations, medians, interquartile ranges, minimums, maximums, and frequency distributions, will be examined for all relevant measures. Transformations of measures will be considered based on distribution diagnostics and outlier analyses. The baseline characteristics of the patients in the entire trial will be described and 95% confidence intervals will be calculated to identify potential differences in baseline characteristics.

- 1. Estimated proportions and means and 95% confidence intervals will be created for each outcome using the data from the entire pilot trial (i.e. combining the data from the two assigned treatment arms).
- 2. Absolute and relative differences for continuous levels and event rates by assigned treatment will be estimated and 95% confidence intervals will be calculated to identify potential treatment differences for safety and for study planning purposes. Subgroup analyses will be exploratory and be based on baseline factors specified prior to the initiation of the trial.
- **3.** Descriptive statistics, including means, standard deviations, medians, interquartile ranges, minimums, maximums, and frequency distributions, will be examined for all relevant measures.

- Transformations of measures will be considered based on distribution diagnostics and outlier analyses.
- The baseline characteristics of the patients in the entire trial will be described and 95% confidence intervals will be calculated to identify potential differences in baseline characteristics.

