Sample Size Justification for Pilot Trial: Assuming a baseline in-hospital mortality risk of 33% in the control arm as was demonstrated in the recently completed PAMPer trial with all cause in-hospital mortality as the primary outcome, enrolling **56 patients in each arm, 112 total patients** and using a 2 sided alpha of 0.05, the study will have a 80% power to detect a 22% (33% to 11%) or greater difference in in-hospital mortality. Based upon current PAMPer clinical outcome data and the additional benefit attributable to LTLR-WB when it is initiated in the prehospital setting, the current proposed mortality difference is clinically meaningful and of sufficient magnitude to influence clinical practice for a pilot trial. The above sample size will provide more than sufficient power for the originally planned feasibility outcomes as we have increased our sample size by 24%. The above power analysis was generated assuming 2 sequential tests using the O'Brien-Fleming spending function to determine test boundaries which are depicted in the following table and graph.

Details	Details when Spending = O'Brien-Fleming, N1 = 56, N2 =56, P1 = 0.1100, P2 = 0.3300							
		Lower	Upper	Nominal	Inc	Total	Inc	Total
Look	Time	Bndry	Bndry	Alpha	Alpha	Alpha	Power	Power
1	0.50	-2.96259	2.96259	0.003051	0.003051	0.003051	0.164669	0.164669
2	1.00	-1.96857	1.96857	0.049002	0.046949	0.050000	0.636252	0.800921
Drift 2.	81024							

Based upon the busy air medical service at the University of Pittsburgh, the bases to be utilized for the pilot trial, 61 patients who met all inclusion and exclusion criteria for the current proposed pilot trial, were admitted to Presbyterian Hospital, consented and were enrolled (www.pamperstudy.com) over a 12 month period 6/2015-5/2016. Based upon a planned enrollment period of 2.5 years, this sample size is feasible after accounting for consent rates and exclusions.

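### Arrival coagulation and platelet-function comparisons have no planned adjustment for pre-injury anticoagulant or antiplatelet use, an avoidable loss of precision rather than a bias

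*Combined protocol and SAP*

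**What the plan says.** Section 1.2 lists presenting coagulopathy among the Aim II outcomes: "multiple organ dysfunction, presenting coagulopathy, 24-hour resuscitation requirements and early mortality as compared to standard of care". Under Mechanistic Outcomes, section 2.8 states "Coagulopathy will be assessed via PT/PTT/INR and rapid Thromboelastography (r-TEG) measurements". Platelet function is assessed in a subset of unstated size, by activation, "aggregation, and adhesion via flow cytometry analysis, whole blood aggregometry measurements and flow chamber analysis". All are to be compared across treatment arms.

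For outcomes in general, section 2.9 says "Absolute and relative differences for continuous levels and event rates by assigned treatment will be estimated", with 95% confidence intervals. It adds a pooled Z test and log-rank tests for mortality, and it allows transformations after distribution and outlier checks. It names no covariate. Its list of outcomes to be recorded omits coagulopathy and platelet function, and so do the Appendix 8 tables.

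Predefined subgroup 6 in section 2.8 is "Those patients with a preinjury history of anticoagulation / antiplatelet therapy", but the subgroup analyses are limited to the primary outcomes. Section 3.3 does not exclude patients on these drugs and admits ages 18 to 89. Section 2.6 randomizes helicopter bases by month, without patient-level stratification. The data-collection list in section 6.5.1 does not name drug history, nor does Appendix 8 Table 1, which has only blank comorbidity rows.

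**The concern.** PT, INR and aggregometry respond to anticoagulant and antiplatelet drugs taken before injury. In an unadjusted comparison that drug effect stays in the residual variance. With about 56 patients per arm, a few more users in one arm move the observed difference.

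The plan treats drug history as relevant to mortality and feasibility. It does not use it for the laboratory measures on which these drugs act most directly. At stake is the precision and readability of the coagulopathy result under Aim II and the platelet-function result under Aim III. The pilot is meant to inform the planning of a larger trial. In an open-label study, a covariate chosen after the data are seen would also be less credible than one named in advance.

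**Working it through.** **The plan's own figure.** Section 2.9 gives a power only for mortality, with "56 patients in each arm, 112 total patients" and the heading "Details when Spending = O'Brien-Fleming, N1 = 56, N2 =56, P1 = 0.1100, P2 = 0.3300". The pooled drift is 0.22 / √(2 × 0.22 × 0.78 / 56) = 2.810. With the stated bounds 2.96259 and 1.96857 the power is 0.801, against 0.800921 in the table. The figure reproduces, and this point does not change it. The documents give no power or precision figure for coagulopathy or platelet function.

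**Inputs.** From the documents: 56 per arm. Assumed, because the documents do not give them: prevalence of drug use, its effect on the measurement, and the spread of INR. The individual-patient formulas below ignore the base-month clustering.

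**Check 1: generic shift.** Let p be the prevalence and d the shift in within-group SDs. Unadjusted variance / adjusted variance = 1 + p(1−p)d². Variance explained = 1 − 1/that ratio. Take a difference that the adjusted analysis detects with 80% power; then unadjusted power = Φ(2.80/√ratio − 1.96).

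| p | d | Ratio | Variance explained | Unadjusted power |
|---|---|---|---|---|
| 5% | 0.5 | 1.012 | 1% | 79.5% |
| 10% | 1.0 | 1.090 | 8% | 76.5% |
| 20% | 1.0 | 1.160 | 14% | 73.9% |
| 20% | 1.5 | 1.360 | 26% | 67.1% |
| 25% | 2.0 | 1.750 | 43% | 56.3% |

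**Check 2: INR scale.** Assume an off-drug mean of 1.3 and an on-drug mean m of 2.2 to 2.5 with SD 0.6. R² = p(1−p)(m−1.3)² / [p(1−p)(m−1.3)² + (1−p)s₀² + p × 0.6²], where s₀ is the off-drug SD. The equivalent sample multiplier is 1/(1−R²).

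- s₀ = 0.3, p = 3%, m = 2.2: 0.0236 / (0.0236 + 0.0981) = 0.19, multiplier 1.24.
- s₀ = 0.3, p = 15%, m = 2.5: 0.1836 / (0.1836 + 0.1305) = 0.58, multiplier 2.41.
- s₀ = 0.6, same two settings: 0.0236 / 0.3836 = 0.06 and 0.1836 / 0.5436 = 0.34, multipliers 1.07 and 1.51.
- SD 0.8 in both groups: 0.0236 / 0.6636 = 0.04 and 0.1836 / 0.8236 = 0.22, multipliers 1.04 and 1.29.

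The off-drug spread therefore drives the answer.

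**Check 3: log scale.** Take the s₀ = 0.3 settings as lognormal, with log variance ln(1 + SD²/mean²).

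- Log variance: 0.052 off drug; 0.072 (mean 2.2) or 0.056 (mean 2.5) on drug.
- Difference in log means: 0.516 (mean 2.2) or 0.652 (mean 2.5).
- p = 3%, mean 2.2: R² = 0.0078 / (0.0078 + 0.0525) = 0.13.
- p = 15%, mean 2.5: R² = 0.0542 / (0.0542 + 0.0525) = 0.51.

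Both are below the raw-scale 0.19 and 0.58.

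**Check 4: chance imbalance.** The SD of the between-arm difference in prevalence is √(2p(1−p)/56): 5.7 points at 10% and 7.6 points at 20%. An imbalance of 10 points or more has probability 8% and 19% respectively.

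At p = 10%, m = 2.5 and s₀ = 0.3, a 1-SD imbalance shifts the INR difference by 0.0567 × 1.2 = 0.068. The unadjusted standard error is √(0.2466 × 2/56) = 0.094 and the adjusted one is √(0.117 × 2/56) = 0.065. Since 0.065² + 0.068² ≈ 0.094², the imbalance is already inside the unadjusted standard error. It is not an additional error.

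**The case against.** The strongest reply is that nothing is wrong. A randomized comparison needs no covariates, and its interval already reflects chance imbalance. That stands: a reader might infer that the coagulation results would be biased, and the documents do not support this. Drug history pre-dates injury and nothing in the design links it to arm.

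A reader might also infer that drug use would dominate INR variance. That needs the narrow off-drug SD of 0.3. Section 2.2 expects 87% arrival shock and 41% coagulopathy, so a wider spread is plausible and the gain then shrinks. Transformation, which section 2.9 allows, reduces it further. No size was derived specifically for r-TEG or platelet function.

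Nor do the documents show that the variable is already collected. Subgroup 6 requires it, but section 6.5.1 and Table 1 do not name it. That the analysis will be unadjusted is likewise read from the absence of any covariate, since section 2.9 does not list these measures at all.

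Two cautions bear on the remedy. History may be missing because a patient died early, and arm might affect early death, so an unknown category is not strictly a baseline level. The platelet-function subset may also be too small to support a covariate.

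The reply that adjustment replaces the protocol's question does not hold for the continuous measures, where a linear model still estimates the arm difference. An adjusted odds ratio for coagulopathy yes/no would be a different quantity, so the point is confined to the continuous measures.

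**Conclusion.** The point holds as a modest precision improvement. The plan compares arrival coagulation and platelet function between arms without a covariate, while drug history, which subgroup 6 requires, is applied only to the primary outcomes. The unadjusted analysis remains valid.

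The size is assumption-dependent: about 1% of variance explained with rare use and a small shift, up to about 40-58% with common use, a large shift and a narrow off-drug spread. In the generic-shift check, a comparison with 80% power after adjustment has 79.5% to 56.3% without it. These figures assume 56 patients per arm and ignore clustering. Base-level clustering, or a smaller platelet-function subset, could widen the imbalance. Because these are secondary and mechanistic outcomes of a pilot, the priority is optional to modest.

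**What to change.** In section 2.9, state that arrival PT/PTT/INR and r-TEG values, on a log scale where skewed, are compared by regression on arm and pre-injury anticoagulant use. Compare platelet function by regression on arm and pre-injury antiplatelet use where the subset size allows. Use standard errors that respect the base-month clusters, and report the unadjusted difference beside each adjusted one.

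Name anticoagulant and antiplatelet history as CRF fields and as Table 1 rows, and ascertain them from sources that pre-date injury. Do not treat unknown history as a true baseline level. Report its frequency by arm and check the result in a sensitivity analysis, for example with unknown counted as no use, or by multiple imputation.

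The cost is SAP wording, the CRF fields and Table 1 rows, one extra model per measure, and some missing history to handle. Sample size, the primary analysis and patient care do not change.

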1.3 BACKGROUND and RATIONALE

Traumatic injury represents an incredible health care burden in the United States and worldwide.¹ Hemorrhage is estimated to be responsible for over 40% of all trauma-related deaths.^{2,3} Ongoing traumatic blood loss is complicated by the well-known 'lethal triad' of coagulopathy, hypothermia and acidosis which results in further unbridled hemorrhage.⁴⁻¹¹ Uncontrolled bleeding, resultant shock and organ dysfunction remain the leading causes of early in-hospital mortality.^{12,13} Despite advances in trauma resuscitation, a paucity of therapeutic interventions are available early enough to reduce the downstream morbidity and mortality attributable to hemorrhage, shock and coagulopathy.^{14,15}

In-hospital resuscitation of traumatic hemorrhage has changed over the past decade.¹⁶⁻²¹ The underlying principle of current resuscitation practice focuses on preventing or reversing the effects of coagulopathy with the early use of a balanced component transfusion strategy (1:1:1 - plasma: packed red blood cells: platelets).²² This reconstituted strategy has also been coined 'whole blood-like' resuscitation despite being inferior compositionally to whole blood.^{23,24} The use of whole blood was historically the gold standard for treating hemorrhagic shock during World War I and II, prior to sweeping changes in blood banking practice.²⁵ Whole blood use continues today and is thought to provide the bleeding patient the identical components they are losing with maximal resuscitative and hemostatic effects.²⁶⁻³⁰

Recent military experiences continue to show the benefits of fresh whole blood resuscitation demonstrating significant survival and hemostatic advantages.³¹⁻³⁴ Whole blood has also been

postulated to improve microcirculatory hemodynamics, reduce the 'storage lesion' effect and minimize donor exposure risks.³⁵ A recent civilian study has also demonstrated benefit using modified whole blood after arrival to the hospital where appropriate blood typing and cross matching was performed prior to transfusion.³⁶ Due to the time sensitive nature of the treatment of hemorrhage, the ideal resuscitation intervention would entail use of a blood product containing all essential hemostatic components, closest to time of injury, where prevention or reversal of the devastating downstream consequences of shock and coagulopathy can occur.

Initiation of whole blood resuscitation in the prehospital setting and continued through the inhospital phase of treatment to patients in hemorrhagic shock represents this ideal intervention post-injury. Essential to the prehospital initiation of whole blood resuscitation in the civilian population is need for it to be transfused without the need for blood typing or cross matching. Of similar importance is the need for cold storage and recycling of any unused whole blood product, allowing maximal utility of this precious resource.

We hypothesize that the initiation of LTLR-WB resuscitation in the prehospital setting with continuation through the in-hospital acute resuscitation phase of care will significantly reduce the morbidity and mortality attributable to hemorrhagic shock post-injury as compared to standard prehospital and in-hospital resuscitation practice. Thus, a large pragmatic clinical trial is needed to definitively establish the efficacy and safety of whole blood resuscitation initiated in the prehospital setting. Only a high-quality clinical trial will provide the essential evidence to justify and provide the impetus for the use of this precious blood banking resource early post-injury. Because of the challenges associated with execution of these types of large trials particularly in the prehospital setting,³⁸ it is essential to establish feasibility of this approach in a pilot study and provide experience to inform a definitive large, multicenter whole blood trial.

